PRIMARY OUTCOME a. iNSPiRED Veterans will improve more in diabetes-related distress (17-item Diabetes Distress Scale). **SECONDARY OUTCOMES** b. iNSPiRED Veterans will improve more in diabetes self-management (Diabetes Self-Management Scale). c. iNSPiRED Veterans will improve more in depression symptoms (Patient Health Questionnaire-8 [PHQ-8]) and anxiety symptoms (Generalized Anxiety Disorder scale [GAD-7]). d. iNSPiRED Veterans will be more likely to use health-promotion programs and clinical care and be more likely to newly choose VHA or community health-promotion programs or clinical care.

STAKEHOLDER OUTCOMES We will employ stakeholder engagement activities to increase development and sustainability of VHA-community partnerships, trust, communication and capacity building. A mixed-methods process evaluation will be used to evaluate this aim.

Section E: Protocol Risks/Subjects

E1. Risk Category

Category 1: Research not involving greater than minimum risk.

E2. Subjects

Gender:

Both

Age:

Adult (18-64 yrs), Geriatric (65+ yrs)

Ethnicity:

All Ethnicities

Primary Language:

English

Groups to be recruited will include:

Asymptomatic patients with chronic conditions, healthy; Patients

Which if any of the following vulnerable populations will be recruited as subjects?

Employees or lab personnel, Mentally ill

Vulnerable populations require special protections. How will you obtain informed consent, protect subject confidentiality, and prevent undue coercion?

Although this study involves minimal risk, particular attention will be given to being sure that participants understand that refusing to consent will not affect eligibility to receive any services or benefits from the VA and that confidentiality will be maintained except as allowed by law or as described in the consent document.

Study staff will contact all referrals by phone for initial screening within 48 hours of the initial contact for those referred by community agencies and Veterans Service Organizations and within 10 days for those recruited through opt out letters. For all patients, a telephone script will be used to obtain verbal consent to administer the initial protocol screening. At the initial screen, the study staff will confirm eligibility criteria. Veterans will be screened for distress using the 2-item screening version of the Diabetes Distress Scale (DDS2). Veterans with a mean score of 3 or more will be eligible for the baseline assessment.

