Patients will be eligible to participate in the study if they meet the following criteria:

(1) Veteran (2) Diagnosis of type 2 diabetes mellitus, per self-report (3) Moderate diabetes-related distress (Diabetes Distress Scale [DDS2] mean score of 3 or greater)

Exclusion Criteria:

(1) Lack of reliable access to a telephone (2) Cognitive, sensory, or other impairment that prevents use of a telephone (3) Current participation in another diabetes-related counseling or self-management program

F2. Procedure

Upon providing informed consent, participants will be randomized in blocks of 6 or 8, based on referral source (MEDVAMC and non-MEDVAMC). At the initial screen, the study staff will confirm eligibility. Veterans will be screened for distress using the 2-item screening version of the Diabetes Distress Scale. Veterans with a mean score of 3 or more will be eligible to continue. Veterans who are eligible and wish to participate further will be scheduled for a telephone baseline assessment. They will be mailed a cover letter, informed consent document without signature lines, and copies of baseline assessment instruments. A member of the study team will call and review the consent documents before final enrollment and completion of the baseline assessment.

Usual care. Veterans randomized to the usual care condition will be encouraged to follow-up with their primary care provider and/or specialty providers for management of their health conditions. They will receive a packet of printed information that includes a list of self-management support resources in the VHA and the local community, but no specific recommendations or referrals. The list will be updated periodically with similar resources as needed.

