
Peer coach selection and training. We will recruit two Veterans through referral from partner agencies and the VHA to serve as peer coaches. Recruitment, hiring, and interviewing will be based on the VHA's peer hiring toolkit. Peer coaches will not have other employment relationships with the VHA. Study investigators will provide 40 hours of training that will cover the role of a peer support provider, general principles of self-management, DM self-management, motivational techniques, goal setting, communication, safety issues and boundaries, and tracking and follow-up procedures. Included will be 8 hours of Military Veteran Peer Network Basic training provided by Mental Health America of Houston, which equips peer coaches with frontline intervention tools (e.g. modes of peer support; assessment skills; skills in handling suicide prevention, stress, and addictive behaviors). Peers will also be oriented to VHA and community DM and mental health resources. A study investigator-clinician readily accessible by phone will supervise coaches, meeting with each one at least weekly. Peers will be provided an intervention manual that includes safety guidelines.

Patient assessments will be measured by telephone by an independent evaluator without access to group assignments at baseline, M3 and M6: -Background and Demographics (baseline) -DM-related distress score, as measured using the DDS17 -Summary of Diabetes Self-care Activities Questionnaire (SDSCA) -The Patient Health Questionnaire-8 (PHQ-8) -The Generalized Anxiety Disorder-7 (GAD-7) -Veteran's self-report of use of community-based or VHA resources (baseline and M6) -Patient Activation Measure (PAM-13) -Patient-Reported Outcomes Measurement Information System (PCORI) instruments: Self-Efficacy for Managing Social Interactions, Emotions, and Daily Activities Participants will be asked if they would like to be mailed a summary of the study results after the study is completed.

Exit interview. We will administer a semistructured exit interview at M6 to intervention group participants to elicit patient-level barriers/facilitators to engagement and views on how to improve the intervention. Questions are designed to elicit

brief responses. Responses will be entered verbatim into the database.

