Outcomes: Secondary outcomes. Analyses of the secondary clinical outcomes will be similar to those used for the continuous primary outcomes. We will test assumptions of normality and make transformations as needed. We will then run linear regression models separately for each secondary outcome. The models will include terms for the intervention, time period, time-by-period interaction, the a priori SES and race/ethnicity variables, and the referral source. Significant values for the time-by-treatment interaction will indicate that there were significant differences over time in the secondary outcome. In addition, by dichotomizing the outcomes, we will determine whether the groups differed in having or not having clinically significant changes in PHQ-8 and GAD-7 scores. A 5.0-point decrease in the value of PHQ-8 will be considered a minimally clinically important change⁹⁴ and coded as such; decreases of less than 5.0 points from baseline will be coded as not having achieved clinically significant change. For GAD-7, a score of less than 10 will be considered as having clinical improvement, with scores of 10 or higher representing clinically elevated anxiety symptoms. We will test whether the two groups (clinically significant change vs. no clinical change) differed using a logistic regression model in which the dichotomous outcomes are the dependent variable. The independent variables will be those described above for the linear regression models.

For the secondary outcomes of use of printed/web-based resources, health promotion programs, and clinical care, we will run logistic regression analyses of dichotomized variables (i.e., whether or not the patient used printed/web resources, whether or not he/she used health promotion programs, and whether or not he/she used clinical care during the 6-month follow-up). The models will include terms for the intervention, the a priori SES and race/ethnicity variables, and the referral source. Significant values for the treatment term will indicate that there were significant differences between the iNSPiRED and usual care groups.

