In examining responses to the Formal Care and Service Utilization questionnaire to determine if iNSPiRED Veterans are more likely to choose VHA or community health care, we will use subsets of the data set. In examining beginning to use care, we will use the subset of participants who did not use VHA services at baseline and completed the 6-month questionnaire. We will determine if each participant did or did not use VHA care at 6 months. A continuity-corrected chi-square test will find any significant differences between the groups in the proportions of users at 6 months. Also, we will run a logistic regression with the outcome of whether or not the Veteran newly used VHA care at 6 months with terms for the intervention, SES, race/ethnicity, and referral source. Then a subset not using community care at baseline will be similarly analyzed.

Exploratory mediator analysis. As noted by Kraemer et al., the mediator must measure change occurring during treatment, must correlate with the intervention, and should have a main or interactive effect on the outcome. The exploratory analysis for examining activation and self-efficacy as possible mediators will include calculation of the correlation between the mediators and treatment. Separate linear models for the primary and secondary outcomes will be run in which the independent variables are the treatment (intervention versus usual care), the potential mediators, and the treatment-by-mediator interactions. Once mediators are identified, a subsequent randomized trial could be designed to help establish if a mediator is indeed a mechanism.

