b) Recruitment through community-based organizations. Several Veterans Service Organizations (e.g. U.S. Vets, Combined Arms) and other Community-based Organizations that serve Veterans (e.g. United Way) will provide venues for diabetes- and mental health-related talks, recruitment opportunities, and posting of flyers. The City of Houston Diabetes Awareness Network has diabetes programs across the City and has agreed to host community talks and post flyers for interested Veterans to contact the study team for more information. Vet Centers have also agreed to post flyers. Flyers will also be distributed through local reserve units, colleges and universities, transitional living centers, independent and assisted living facilities, outpatient clinics, other community groups, at resource fairs, and the Harris County and City Jails (to unincarcerated Veterans only). In some cases, flyers will be made available directly to Veterans and in other cases through a case manager. The United Way will also send a text blast to Veterans in their program (see text message in Section S).

c) Opt-out letters. We will request from the VA Corporate Data Warehouse a list of patients of MEDVAMC who have had at least one visit in the past year with an ICD 10 code for Type 2 DM (E11.x). We will also request a list of patients with an ICD 10 code for Type 2 DM (E11.x) with at least one visit in the past 3 years but no visits in the past year. Variables requested will be name, address, phone numbers, E11.x diagnosis code, Scrambled SSN and Real SSN. Real SSN is needed in order to search for updated contact information if needed. These subjects will be mailed a letter that describes the purpose of the study, provides contact information for study staff, and invites them to opt-out (a toll-free number will be provided) to the study (opt-out letters). Veterans who do not opt out will be called by study staff for screening and consent.

This query will be repeated every six months during the recruitment period. In addition, flyers will be posted at MEDVAMC and providers in the Primary Care and Specialty Clinics and the pharmacy will be provided flyers and asked to refer interested patients to the study.

CONTINUED IN SECTION S

Are foreign language consent forms required for this protocol?

No

J3. Privacy and Intrusiveness

Will the research involve observation or intrusion in situations where the subjects would normally have an expectation of privacy?

No

J4. Children

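### The logistic models for use of health-promotion programs and of clinical care leave out baseline use; prespecifying it may recover a little power on a secondary outcome

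*Combined protocol and SAP*

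**What the plan says.** Secondary outcome (d) in Section D has two halves. The first is that intervention Veterans will use health-promotion programs and clinical care more. The second is that they will "be more likely to newly choose VHA or community health-promotion programs or clinical care".

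For the first half, G2 (Outcomes: Secondary outcomes) defines binary endpoints: "whether or not he/she used health promotion programs, and whether or not he/she used clinical care during the 6-month follow-up". A third model of the same form covers printed and web resources, which Section D does not list under (d). For all three: "The models will include terms for the intervention, the a priori SES and race/ethnicity variables, and the referral source".

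The second half is analysed separately in G2, by restriction. For VHA care, "we will use the subset of participants who did not use VHA services at baseline and completed the 6-month questionnaire". For community care, "Then a subset not using community care at baseline will be similarly analyzed".

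Three other places bear on the point:

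- The patient assessments in F2 include the Veteran's "self-report of use of community-based or VHA resources (baseline and M6".
- G2 (Outcomes: Primary outcome) declines to adjust for baseline characteristics on which the arms turn out to differ. It admits SES and race/ethnicity because they are named a priori.
- The continuous outcomes enter a repeated-measures model with baseline as one of the time points, so they already carry their own baseline value.

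**The concern.** Past use of a service is a natural predictor of later use. When a baseline covariate predicts a binary outcome, a logistic test that leaves it out has less power than one that includes it, and the single-trial estimate moves with any chance imbalance in prior users. The plan already collects some form of baseline use and relies on it for the new-user subsets, yet the models for overall use ignore it. The plan's own rule against adjusting for observed differences closes the door later: if prior users turn out unevenly split, the term cannot be added.

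What is at stake is some efficiency on the first half of (d). Section G1 bases the sample size on DDS17, PHQ-8 and GAD-7 only, so nothing protects power for the use outcomes.

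**Working it through.** **The plan's own figure.** G1 gives no power, use rate or effect size for the use outcomes. What it does state reproduces with the normal approximation, 2((z0.975 + z0.80)/d)², multiplied by [1 + (2 − 1)0.5]/2 = 0.75 and divided by (1 − 0.30):

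- d = 0.50: 62.79 × 0.75 = 47.09; 47.09 / 0.70 = 67.3 (stated: 67 per group, 134 in all).
- d = 0.80: 24.53 × 0.75 = 18.4; 18.4 / 0.70 = 26.3, rounded up to 27 (stated: 18.4 and 27).
- 134 × 1.627 = 218.

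This point challenges none of these.

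**Inputs.** From the documents: 218 recruited 1:1, 30% attrition, two-sided 5%. Completers per arm: 218 / 2 × 0.70 = 76.3, taken as 76. At that size, 80% power needs roughly 30% vs 53% or 50% vs 72%. Assumed, because the documents are silent: use rates, prevalence of prior use, and phi between prior and later use.

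**Simulation.** 20,000 trials per setting. Follow-up use is fixed by arm and phi is set in the control arm. Both models contain arm, referral source and one binary SES-type covariate; one adds baseline use. Likelihood-ratio test at 5%. Monte Carlo standard error of each power figure: √(0.70 × 0.30 / 20,000) = 0.3 points.

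| Prior use | Follow-up use | phi | Power without | Power with | Gain |
|---|---|---|---|---|---|
| 40% | 40 vs 60% | 0 | 70.0 | 70.0 | 0.0 |
| 40% | 40 vs 60% | 0.1 | 69.9 | 70.5 | 0.6 |
| 40% | 40 vs 60% | 0.2 | 69.7 | 71.7 | 2.0 |
| 40% | 40 vs 60% | 0.3 | 69.9 | 73.7 | 3.8 |
| 10% | 40 vs 60% | 0.1 | 70.2 | 70.5 | 0.3 |
| 10% | 40 vs 60% | 0.2 | 70.0 | 71.6 | 1.6 |
| 10% | 40 vs 60% | 0.3 | 70.2 | 72.9 | 2.7 |
| 5% | 40 vs 60% | 0.1 | 69.9 | 70.2 | 0.3 |
| 5% | 40 vs 60% | 0.2 | 69.6 | 70.7 | 1.1 |
| 95% | 85 vs 95% | 0.1 | 57.5 | 57.5 | 0.0 |
| 95% | 85 vs 95% | 0.2 | 56.8 | 58.1 | 1.3 |
| 95% | 85 vs 95% | 0.3 | 57.1 | 61.0 | 3.9 |

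- *Prior use partly carried by other terms* (correlation 0.5 with referral source, 0.3 with the SES-type covariate; 40% prior use): 70.1 to 71.2 at phi 0.2; 71.3 to 74.2 at phi 0.3.
- *Strong prediction* (40% prior use, phi 0.5): 70.1 to 81.3. This phi is impossible at low prevalence. The ceiling is √[pb(1 − py) / (py(1 − pb))], with pb prior use and py follow-up use. For py = 0.40 it is √(0.06/0.36) = 0.41 at pb = 0.10 and √(0.03/0.38) = 0.28 at pb = 0.05.
- *Test size.* Null rejection is 4.9–5.4% without the term and 5.1–5.7% with it.
- *Precision* (40% prior use, phi 0.3). The standard error of the log odds ratio rises from 0.337 to 0.358 (6%), while the median estimate moves from 0.83 to 0.92. The standard error of the standardized risk difference falls from 0.0797 to 0.0766 (4%).
- *Chance imbalance.* The exact binomial chance of a gap of 10 points or more in prior users is 21.4% at 40% prior use, 4.2% at 10%, and 0.6% at 5% or 95%. At 40% prior use and phi 0.3 the slope of the unadjusted risk difference on the imbalance is 0.29, so a 10-point gap shifts it by 0.29 × 10 = 2.9 points; the adjusted slope is 0.00.

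**Second check, other rates.** Wald test, 3,000 trials per setting, prior use 30%, 50% or 80%, follow-up use 30 vs 52.5%, 50 vs 72% or 40 vs 55%. The gain is 0–2 points at a prior-use odds ratio of 2, 2–4 at 4, 4–11 at 10 and 6–22 at 25. One setting with phi only 0.30 gained 5.9 points, but it pairs 80% prior use with an odds ratio of 25.

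**The case against.** The planned analysis is valid. Its covariates are prespecified and referral source, the randomization stratifier, is among them. One more prognostic term is good practice, not a correction. That stands, and it makes the point minor.

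The design also limits the loss. Section F1 excludes those with "Current participation in another diabetes-related counseling or self-management program", so prior use of the most relevant programs may be uncommon. Part of the MEDVAMC pool in J2 is drawn from "patients of MEDVAMC who have had at least one visit in the past year", so prior clinical care may be near universal there. Referral source is a partial proxy for VHA use. All this stands: the rare and near-universal rows with weak prediction show a gain of about zero. A reader might infer that omission costs power whenever prior use predicts later use. The row at 95% prior use and phi 0.1 shows otherwise.

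The matching covariate may not exist. F2 describes use by where it took place, and does not say that health-promotion and clinical-care use are separate items. The VHA-use and community-use indicators would then be a weaker stand-in. If such a proxy correlates 0.5 with the matching item (an assumption), phi 0.3 becomes 0.3 × 0.5 = 0.15, which falls between gains of 0.6 and 2.0 points in the 40% rows; a direct simulation gave about 0.7. This stands too, and limits what the fallback can deliver.

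None of this gives a reason to leave out a matching item if one is recorded.

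**Conclusion.** The point holds as a minor efficiency matter on a secondary outcome with no stated power. Under the assumed rates (76 completers per arm, 40% vs 60% use), leaving out baseline use costs about 0 to 4 points of power for phi 0 to 0.3. The cost is about zero where prior use is rare or near universal and weakly predictive. It reaches about 11 points at 40% prior use and phi 0.5, that is, only if prior use is common and strongly predictive. The documents do not say which case applies.

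Three stronger readings are not supported:

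- *That the planned test is biased or has the wrong size.* Randomization protects it, and the simulated null rejection is close to 5%.
- *That adjustment would narrow the interval for the odds ratio.* The standard error of the log odds ratio rises. The power gain comes from a conditional estimate further from zero, and the precision gain applies only to the standardized risk difference.
- *That the newly-choose half of (d) shares the omission.* G2 handles it by restricting to baseline non-users.

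**What to change.** 1. Confirm which use items the baseline questionnaire records: health-promotion programs, clinical care, and printed or web resources.
2. Where a matching item exists, name it in G2 as an a priori covariate in the corresponding use model, and keep the other terms.
3. If only the VHA-use and community-use indicators exist, they may be used instead, with a likely gain under about 2 points.
4. State that the odds ratio is conditional on baseline use, and report a standardized risk difference with its confidence interval beside it.
5. Fix one estimation method for sparse cells in advance, with no switch triggered by the data. In the simulations a baseline-use category was all or none on the outcome in 17% of trials at 10% prior use and phi 0.3, 38% at 5% and phi 0.2, 9% at 95% and phi 0.2, and 0% at 40% and phi 0.3. The power figures above rest on ordinary likelihood-ratio tests; a penalized method such as Firth's was not evaluated.

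The imputation paragraph of G2 already takes in all variables of the substantive analyses, so baseline use follows once it is a model term.

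The cost is a few sentences in G2 and a check of the questionnaire, with no new data if the items or the indicators are recorded. The small downsides are one more model term and a changed odds-ratio target.

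### The planned test of newly chosen care measures only first entry into the VHA or into community care, which is narrower than secondary outcome d

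*Combined protocol and SAP*

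**What the plan says.** Section D lists, as secondary outcome d, that intervention Veterans will use programs and care more, and will "be more likely to newly choose VHA or community health-promotion programs or clinical care". The outcome names programs as well as clinical care, and it is not limited to Veterans outside the VHA.

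G2 Data Analysis treats the two limbs separately.

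- **Any use.** Logistic models in all participants cover printed or web resources, "whether or not he/she used health promotion programs, and whether or not he/she used clinical care during the 6-month follow-up".
- **New use.** Using the Formal Care and Service Utilization questionnaire, "we will use the subset of participants who did not use VHA services at baseline and completed the 6-month questionnaire". The outcome is system-wide: "We will determine if each participant did or did not use VHA care at 6 months". The test is stated as "A continuity-corrected chi-square test will find any significant differences between the groups in the proportions of users at 6 months", with a supporting logistic regression. For the other system, "Then a subset not using community care at baseline will be similarly analyzed".

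F2 Procedure collects self-reported VHA and community resource use at baseline and month 6, without a look-back period. J2 Consent Procedures recruits by opt-out letter from "a list of patients of MEDVAMC who have had at least one visit in the past year", and also from a second list of patients seen within three years but not in the past year. The exclusion criteria in F1 Design bar "Current participation in another diabetes-related counseling or self-management program".

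**The concern.** The objective concerns newly taking up programs or care. The analysis concerns going from no use of a whole system to some use of it. The two agree for a Veteran who uses neither system at baseline. They part for anyone who already uses one system and newly starts something else within it.

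F2 describes coaches connecting Veterans with VHA services, community services or both, including diabetes education, dietitians and counselling. New uptake inside a system the Veteran already uses is therefore one of the effects the intervention could have. The new-use test cannot see that effect. It could show no difference in new VHA use even if coaching brought many VHA patients into VHA programs for the first time. The test may also rest on a small part of the sample, and no power is stated for it.

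**Working it through.** **1. Who can count where.** Applying the G2 rules to each baseline status gives:

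| Baseline use | Event by month 6 | VHA new-use test | Community new-use test | Any-use models |
|---|---|---|---|---|
| VHA only | First VHA program | Excluded | Included, not an event | User |
| VHA only | First community care | Excluded | Event | User |
| Community only | First VHA care | Event | Excluded | User |
| Community only | First community program | Included, not an event | Excluded | User |
| Both | Any new program or service | Excluded | Excluded | User |
| Neither | First VHA care | Event | Included, not an event | User |

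Rows 1, 4 and 5 are new choices within outcome d that register nowhere as new. The any-use models separate neither new from continuing use nor VHA from community use. This step needs no assumption.

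**2. The plan's own sample size does not cover this test.** G1 Sample Size reproduces with the normal approximation (two-sided 0.05, 80% power, adjustment factor [1 + (2 − 1) × 0.5]/2 = 0.75, 30% attrition).

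- DDS17, d = 0.50: 62.8 × 0.75 / 0.70 = 67.3 per group, against the plan's 67 (134 in total).
- PHQ-8 and GAD-7, d = 0.80: 24.5 × 0.75 = 18.4, then 18.4 / 0.70 = 26.3, so 27 per group. That is 54 in total, or about 25% of 218.

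Neither calculation concerns service use.

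**3. Size of the VHA subset.** Expected completers are 218 × 0.70 = 152.6. If a share s uses the VHA at baseline, the subset is 152.6 × (1 − s). The documents give no s.

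- s = 0.50: 76.3, about 38 per arm.
- s = 0.80: 30.5, about 15 per arm.

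A wider range follows from a MEDVAMC share m, a VHA non-user fraction u among MEDVAMC recruits and v among community recruits: 152.6 × [m·u + (1 − m)·v]. With m from 0.25 to 0.75, u from 0 to 0.5 and v from 0.5 to 1.0 (all assumed), the subset runs from about 19 to 134.

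**4. Power of the planned test.** These are exact binomial results for the continuity-corrected chi-square at two-sided 0.05. The 20% and 40% uptake rates are assumptions.

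| Per arm | Power, 20% vs 40% | Rate detectable from 20% at 80% power |
|---|---|---|
| 38 | 0.38 | about 53% |
| 15 | 0.10 | about 76% |
| 76 (all completers) | 0.72 | about 42% |

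The last row is an upper bound for a category-based analysis, before removing those already using the category. At an assumed 10% versus 20%, 76 per arm gives only 0.33.

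**The case against.** The system-entry question is coherent and appears deliberate. G2 describes it as examining who begins to use care, and Section D and F1 stress reaching Veterans outside the VHA. Outcome d does not define newly choosing. The any-use models cover everyone, and the exclusion of current diabetes counselling or self-management participants means that later use of such a program is largely new use. For diabetes programs, then, the main loss is the VHA or community label. All of this stands. It supports keeping the entry analysis, but it does not make that analysis cover the programs that outcome d names.

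Three stronger readings are tempting, and the documents do not support them.

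- **That most MEDVAMC recruits are removed.** This is plausible if the past-year list supplies most of them, but no split is given. The second list consists of lapsed patients, who may qualify as non-users depending on the unstated look-back.
- **That a VHA patient's new program is never counted.** It is counted in the any-use models, only not as new or as VHA use.
- **That linking VHA patients to VHA services is the coach's main task.** F2 gives VHA and community resources together, with many community examples.

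A finer definition also does not guarantee better power. Splitting by category lowers event rates, and the 0.33 above is below the 0.38 at 38 per arm, although the two rest on different assumed rates. The exclusion criterion places nearly everyone at risk for diabetes programs only. For clinical care the at-risk group will be smaller.

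**Conclusion.** The mismatch is real and can be read from the text: outcome d covers newly chosen programs or care in either system, while the new-use analysis tests first entry into a system. Uptake within a system already in use, and any new choice by a dual user, cannot register as new.

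The extent is undocumented. With 50% to 80% VHA use at baseline and 30% attrition, about 76 to 31 participants remain, with about 38% to 10% power for 20% versus 40%. The baseline share and both uptake rates are assumptions. The mismatch does not depend on them.

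This affects one limb of one secondary outcome. The DDS17 analysis and its sample size are untouched. It is a cheap improvement, worth making before outcome data are examined by arm so that the definition is not chosen afterwards.

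**What to change.** In G2, in the paragraph on the Formal Care and Service Utilization questionnaire:

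1. Add an analysis of new use for the two categories that the any-use models already separate, health-promotion programs and clinical care. Do this for the VHA and for the community, which gives four comparisons.
2. For each, take as at risk the month 6 completers who were not using that category in that system at baseline, whatever else they used there.
3. State one look-back period and use it at both baseline and month 6. Say how lapsed VHA patients are classified.
4. Keep the present analysis, labelled as first entry into VHA or community care.
5. Report the expected and actual size of each at-risk group.

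This needs wording and coding of data already collected, with no new patients or visits. The costs are a few more secondary comparisons, to be reported as such, and lower event rates per category. It also relies on the questionnaire recording service type by system. The separate outcomes in G2 suggest that it does, but the instrument is not shown. One limit remains: a Veteran already receiving VHA clinical care who newly starts VHA mental health care would still not count as new under the broad clinical-care category.
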